## 5.5.2 Analysis of Secondary Variables

The secondary variables will be tested in an exploratory manner and p-values will not be considered confirmatory. No multiplicity adjustments will be conducted. Same MMRM models with MAR assumption defined for the primary analysis will be fitted for the next secondary efficacy endpoints: total score and Domain 4 of KPSS, Domain A, Domain B, Domain K and total score of MDS-NMS, MDS-UPDRS part III and part IV separately, and PDQ-8. The LS means associated with treatments and treatment differences will be presented with 95% confidence intervals and corresponding p-values for each visit.

#### 5.5.2.1 Total Score and Domain 4 of KPPS

The KPPS questionnaire description, summary and listing are already presented in Section 5.5.1.

Domain 4 consists of 2 questions about nocturnal pain.

Change from baseline in total score and Domain 4 score will be analysed using MMRM as described in Section 5.5.1.

I-DM-011SAP Page 26 of 49

The following statistical output will be provided:

Table 15.2.2.1.1 Analysis of the Domain 4 of KPPS – Full Analysis Set

Table 15.2.2.1.2 Analysis of the Domain 4 of KPPS – Per-Protocol Set

Table 15.2.2.2.1 Analysis of KPPS Total Score – Full Analysis Set

Table 15.2.2.2.2 Analysis of KPPS Total Score – Per-Protocol Set

The LS means associated with treatments and treatment differences will be presented with 95% confidence intervals and corresponding p-values.

#### 5.5.2.2 Movement Disorder Society-sponsored Non-motor Rating Scale

The Movement Disorder Society-sponsored Non-motor Rating Scale (MDS-NMS) consists of 13 domains: depression (A), anxiety (B), apathy (C), psychosis (D), impulse control and related disorders (E), cognition (F), orthostatic hypertension (G), urinary (H), sexual (I), gastrointestinal (J), sleep and wakefulness (K), pain (L), other (M). In addition, a subscale for non-motor fluctuations to assess changes in non-motor symptoms in relation to the timing of anti-PD medications across 8 domains.

The MDS-NMS will be filled out at Visit 2b, Visit 4, Visit 5 and Visit 6/EDV.

Each questionnaire item is scored for frequency and severity:

- Frequency:
  - 0 Never
  - 1 Rarely
  - 2 Sometimes
  - 3 Frequently
  - 4 Majority of time
- Severity
  - 0 Not present
  - 1 Minimal
  - 2 Mild
  - 3 Moderate
  - 4 Severe

Then item score is calculated as frequency multiplied by severity. A domain total score will be calculated as sum of all items. If any item score is missing, then corresponding domain score will not be calculated.

The total score will be calculated by summing the domains from A to M. In case, where any domain score is missing, then total score will not be calculated.

The lower total scores represent better quality of life.

Change from baseline in total score, domain A (depression), domain B (anxiety) and domain K (sleep and wakefulness) score will be analysed using MMRM as described in Section 5.5.1.

The following statistical output will be provided:

## Table 15.2.3.1.1 Summary of MDS-NMS – Full Analysis Set

Table 15.2.3.1.2 Summary of MDS-NMS – Per-Protocol Set

The MDS-NMS domains and total scores will be summarised by visit, including changes from baseline, using default summary statistics.

Table 15.2.3.2.1 Analysis of MDS-NMS – Full Analysis Set

Table 15.2.3.2.2 Analysis of MDS-NMS – Per-Protocol Set

The LS means associated with treatments and treatment differences will be presented with 95% confidence intervals and corresponding p-values for each visit using MDS-NMS total score, Domain A, Domain B and Domain K score.

I-DM-011SAP Page 27 of 49

## Listing 16.2.3.2 MDS-NMS – Enrolled Set

MDS-NMS each question of domain, domain and total scores will be displayed for each patient in the enrolled set.

#### 5.5.2.3 Movement Disorder Society-sponsored Unified Parkinson's Disease Rating Scale

The Movement Disorder Society-sponsored Unified Parkinson's Disease Rating Scale (MDS-UPDRS) consists of 4 parts:

- Part IA and IB: Non-Motor Aspects of Experiences of Daily Living (nM-EDL) (13 questions)
- Part II: Motor Aspects of Experiences of Daily Living (M-EDL) (13 questions)
- Part III: Motor Examination (33 items based on 18 questions)
- Part IV: Motor Complications (6 questions).

Part I and Part II will be filled out only once at Visit 2b. Part III and Part IV will be filled out at Visit 2b, Visit 4, Visit 5 and Visit 6/EDV. Every item can be scored on a 5-point scale: 0 ("normal"), 1 ("slight"), 2 ("mild"), 3 ("moderate"), 4 ("severe"), with higher scores indicating more severe impairment. The maximum total MDS-UPDRS score is 260, indicating the worst possible disability from PD.

The total score for each part will be calculated as the sum of each item. According to Goetz et al. [4], valid score for the MDS-UPDRS parts can be calculated if the respective part contains a number of missing values less than or equal to the following:

- Part I − 1
- Part II − 1
- Part III 3
- Part IV − 0

For patients with partially missing data, a prorated score will be calculated by taking the mean of the observed scores and multiplying it by the total number of items in each part. The prorated score will be rounded to the nearest whole number. Otherwise, total score for that part will be set to missing.

Change from baseline in Part III and Part IV will be analysed using MMRM as described in Section 5.5.1

The following statistical output will be provided:

## Table 15.2.4.1.1 Summary of MDS-UPDRS – Full Analysis Set

## Table 15.2.4.1.2 Summary of MDS-UPDRS – Per-Protocol Set

The MDS-UPDRS parts and total scores will be summarised by visit, including changes from baseline, using default summary statistics.

## Table 15.2.4.2.1 Analysis of MDS-UPDRS Part III/IV Total Score – Full Analysis Set

## Table 15.2.4.2.2 Analysis of MDS-UPDRS Part III/IV Total Score – Per-Protocol Set

The LS means associated with treatments and treatment differences will be presented with 95% confidence intervals and corresponding p-values.

#### Listing 16.2.3.3.1 MDS-UPDRS – Enrolled Set

MDS-UPDRS items and total scores will be displayed for each patient in the enrolled set.

## Listing 16.2.3.3.2 MDS-UPDRS Part III Additional Information – Enrolled Set

MDS-UPDRS part III additional information about medication, clinical state, dyskinesias impact, Hoehn and Yahr stage will be displayed for each patient in the enrolled set.

#### 5.5.2.4 Parkinson's Disease Questionnaire

The Parkinson's Disease Questionnaire (PDQ-8) will be filled out at Visit 2b, Visit 4, Visit 5 and Visit 6/EDV. The questionnaire contains eight aspects: mobility, activities of daily live, emotional wellbeing, stigma, social support, cognitions, communication and bodily discomfort. Every question is rated on a 5-point scale: 0 ("never"), 1 ("occasionally"), 2 ("sometimes"), 3 ("often"), 4 ("always or cannot do at all"). The PDQ-8 index will be calculated as follows:

I-DM-011SAP Page 28 of 49

PDQ-8 index = 
$$\frac{Sum \ of \ items}{Maximum \ possible \ score} \times 100$$
,

where the maximum possible score is 32. If one item answer is missing, then PDQ-8 index will not be calculated. The higher index scores indicate more difficulty due to having PD.

Change from baseline in PDQ-8 index will be analysed as described in Section 5.5.1.

The following statistical output will be provided:

Table 15.2.5.1.1 Summary of PDQ-8 Index – Full Analysis Set

Table 15.2.5.1.2 Summary of PDQ-8 Index – Per-Protocol Set

The PDQ-8 index will be summarised by visit, including changes from baseline, using default summary statistics.

Table 15.2.5.2.1 Analysis of PDQ-8 Index – Full Analysis Set

Table 15.2.5.2.2 Analysis of PDQ-8 Index – Per-Protocol Set

The LS means associated with treatments and treatment differences will be presented with 95% confidence intervals and corresponding p-values.

Listing 16.2.3.4 PDQ-8 – Enrolled Set

PDQ-8 items and index will be displayed for each patient in the enrolled set.

#### 5.5.2.5 Clinical Global Impression of Change and Patient's Global Impression of Change

The Clinical Global Impression of Change (CGIC) scale requires the investigator to assess how much the patient's overall status has improved or worsened since the start of the study. The Patient's Global Impression of Change (PGIC) consists of a general evaluation of patient own overall status in comparison to the start of the study. Both questionnaires will be evaluated at Visit 4, Visit 5 and Visit 6/EDV.

The CGIC and PGIC will be rated on a 7-point scale: 1 ("very much improved"), 2 ("much improved"), 3 ("minimally improved"), 4 ("no change"), 5 ("minimally worse"), 6 ("much worse"), 7 ("very much worse").

Improvement analysis will be performed. Parameters will be categorised into 2 groups based on response given: improved (which include answers from 1 to 3) and not improved (answers from 4 to 7). The number of responses (improved vs. not improved) will be compared among two treatment groups using Fisher's exact test. The following SAS code will be used:

The following statistical output will be provided:

Table 15.2.6.1.1 Summary of CGIC and PGIC – Full Analysis Set

Table 15.2.6.1.2 Summary of CGIC and PGIC – Per-Protocol Set

CGIC and PGIC will be summarised for each visit where assessments were made.

Table 15.2.6.2.1 Improvement Analysis of CGIC and PGIC – Full Analysis Set

Table 15.2.6.2.2 Improvement Analysis of CGIC and PGIC – Per-Protocol Set

Improvement groups of CGIC and PGIC will be summarised for each visit where assessments were made. Odds ratio, 95% CI and P-values of Fisher's exact test by visit will be provided.

Listing 16.2.3.5 CGIC and PGIC – Safety Set

The CGIC and PGIC data will be displayed for each patient in the safety set.

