#### **Statistical methods:**

The analyses of all efficacy endpoints will be based on the full analysis set (primary analysis population) and per-protocol set for sensitivity purpose.

The primary efficacy endpoint (change from baseline to V6 in the Domain 3 of KPPS) will be analysed using Analysis of Covariance (ANCOVA) with treatment as fixed factor and baseline KPPS as a covariate to demonstrate superiority of opicapone against placebo.

The key secondary endpoint (change from baseline in Domain B [anxiety] of MDS-NMS) as well as all other secondary efficacy endpoints will be analysed in an exploratory manner by treatment arm using appropriate parametric or non-parametric statistical methods. Descriptive statistics including 95%-confidence intervals will be presented per treatment arm. Potential sensitivity analyses will be specified in the *statistical analysis plan* (*SAP*).

The analyses of all safety endpoints will be based on the safety set.

All AEs will be summarised by number and percent of patients with AEs. Treatment-emergent AEs (TEAEs) will be summarised by calculating the number and percent of patients with AEs by preferred term (PT) and system organ class (SOC). TEAEs will also be summarised by severity and relationship to treatment. Number and percent of patients with serious TEAEs,

related serious TEAEs and TEAEs leading to discontinuation from study will be provided by SOC and PT. All AEs, SAEs and TEAEs leading to study termination will be listed.

Vital signs and laboratory parameters will be summarised by calculating summary statistics on the absolute values and on the change from baseline. Abnormal values will be assessed as clinically significant or not clinically significant.

Summary statistics and shift tables will be performed for physical examinations and, neurological examinations. Abnormal values will be assessed as clinically significant or not clinically significant.

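### The only planned between-arm test of CGIC and PGIC is Fisher's exact test on improved versus not improved; an ordinal comparison on the seven categories should stand beside it

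*SAP*

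**What the plan says.** SAP 5.5.2.5 states that "The CGIC and PGIC will be rated on a 7-point scale", from 1 (very much improved) to 7 (very much worse), at Visits 4, 5 and 6/EDV. Responses are then grouped as "improved (which include answers from 1 to 3) and not improved (answers from 4 to 7", and the groups "will be compared among two treatment groups using Fisher's exact test". For the output it says "Odds ratio, 95% CI and P-values of Fisher's exact test by visit will be provided". A separate pair of tables is descriptive: "CGIC and PGIC will be summarised for each visit where assessments were made".

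The list of tables in SAP 10.1 agrees. For these two scales it contains only Summary tables (15.2.6.1.1 and 15.2.6.1.2) and Improvement Analysis tables (15.2.6.2.1 and 15.2.6.2.2), each for the full analysis and per-protocol sets.

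On status, SAP 5.5.2 says "The secondary variables will be tested in an exploratory manner and p-values will not be considered confirmatory", with no multiplicity adjustment. The protocol synopsis lists CGIC and PGIC themselves as secondary endpoints, not the proportion improved, and leaves the method open: "appropriate parametric or non-parametric statistical methods".

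**The concern.** The comparison treats a minimal improvement like a very large one, and no change like severe worsening. A treatment effect that moves patients within either group adds nothing to the test. The other rating scales (KPPS, MDS-NMS, MDS-UPDRS Parts III and IV, PDQ-8) are compared as full scores by MMRM, so CGIC and PGIC are the rating scales tested only after collapsing.

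Fisher's exact test adds a second loss, because with a discrete 2×2 table it rejects less often than its nominal level. What is at stake is the precision of two global measures that readers use to judge whether a change in pain score matters to the patient.

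**Working it through.** **1. The plan's own figures.** The documents give no power, category distribution or effect size for CGIC or PGIC. The only sizing is for KPPS Domain 3 (SAP 2.6), and it reproduces:

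- n per arm = 2 × (1.960 + 0.842)² × (5.8/3.0)² = 58.7, so 59 by the normal approximation. The exact t-test has 80.2% power at 60 per arm, which matches 2 × 60.
- 120/0.85 = 141.2, so 142 against the stated 140.

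**2. Inputs.**

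- From the SAP: seven categories, the split 1–3 versus 4–7, and 122 patients in the full analysis set.
- Assumed: two-sided 0.05; 61 per arm (122/2; the split by arm is not given); and these placebo distributions over categories 1 to 7:

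| Placebo improved | 1 | 2 | 3 | 4 | 5 | 6 | 7 |
|---|---|---|---|---|---|---|---|
| 30% | .01 | .07 | .22 | .45 | .17 | .06 | .02 |
| 40% | .02 | .12 | .26 | .38 | .14 | .06 | .02 |
| 50% | .03 | .15 | .32 | .33 | .11 | .05 | .01 |
| 60% | .05 | .20 | .35 | .25 | .09 | .05 | .01 |
| 45%, few categories used | 0 | .05 | .40 | .50 | .05 | 0 | 0 |

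**3. Formulas.**

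- Proportional odds: each cumulative probability c becomes c′ = OR·c / (1 − c + OR·c).
- Fisher power: the sum over all a, b of Bin(a; 61, p₁) × Bin(b; 61, p₂) over the tables with Fisher p ≤ 0.05. This is exact.
- Ordinal power: tie-corrected Wilcoxon rank-sum test, 40,000 simulated trials per scenario.
- Relative loss = 1 − Fisher power / Wilcoxon power.

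Example, placebo 40% improved and OR 2.0: c′ = 0.80/(0.60 + 0.80) = 0.57. Fisher power is 42.6% and Wilcoxon 56.1%, so the loss is 13.5 points, or 1 − 42.6/56.1 = 24%.

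**4. Results: Wilcoxon % / Fisher % (relative loss).**

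| Placebo improved | OR 1.5 | OR 2.0 | OR 2.5 | OR 3.0 |
|---|---|---|---|---|
| 30% | 22.9 / 13.7 (40%) | 54.4 / 38.3 (30%) | 78.0 / 63.3 (19%) | 90.8 / 80.5 (11%) |
| 40% | 23.1 / 16.2 (30%) | 56.1 / 42.6 (24%) | 79.3 / 66.2 (16%) | 91.4 / 81.6 (11%) |
| 50% | 23.4 / 16.2 (31%) | 55.9 / 40.4 (28%) | 79.2 / 62.2 (21%) | 91.2 / 77.2 (15%) |
| 60% | 23.8 / 13.9 (42%) | 55.9 / 35.1 (37%) | 79.3 / 55.5 (30%) | 91.5 / 70.4 (23%) |
| 45%, few categories | 21.0 / 16.6 (21%) | 50.8 / 42.3 (17%) | 74.3 / 64.9 (13%) | 87.9 / 79.9 (9%) |

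The loss runs from 4 to 24 percentage points, or 9% to 42% in relative terms. A latent normal shift equal to the primary sizing effect, 3.0/5.8 = 0.52 SD, gives Wilcoxon 71–77% against Fisher 50–57%, a loss of 21–35%.

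**5. How much is the split and how much is Fisher.** With no effect, Fisher's true size is 3.1–3.7% and the Wilcoxon test's is 4.9–5.1%. An uncorrected chi-square test on the same split loses between −3% and 25% under proportional odds. The rest of the gap is Fisher's conservatism.

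**6. Effects that are not a common shift (placebo 40% improved).**

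- 20 points moved only from category 4 to 3: Fisher 55%, Wilcoxon 25%.
- 20 points moved only from category 3 to 2: Fisher 3.3% (its size), Wilcoxon 12%.

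**The case against.** The strongest reply has five parts.

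*The endpoints are exploratory.* This is true: they have no power target, the protocol leaves the method open, and the SAP's choice is within it. An improved/not-improved proportion is easy to read and comes with an odds ratio and 95% CI. This limits the importance of the point. It does not explain why the ordering should go untested, and without multiplicity adjustment an added ordinal analysis costs no alpha elsewhere.

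*The ordinal test is not always better.* This stands. Step 6 shows Fisher's test well ahead when the effect sits exactly at the cut, and nothing in the documents says which pattern to expect. It is the reason to keep the split, though not to make it the only test.

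*A fixed loss of about a third.* A reader might infer this. The documents supply no figure from which to derive it, and in the table it appears only with smaller effects or a high placebo improvement rate. At OR 3.0 the loss is 9–23%.

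*Invisible shifts, or a probable false negative.* A reader might also infer these, and neither is supported. Category counts and percentages by arm are the default summary (SAP 4.1 and 4.3), so a shift within a group would be shown, only not tested. The event that matters is a significant Wilcoxon test with a non-significant Fisher test. Simulated at 58 per arm with placebo improvement of 25%, 40% and 55%, it occurs in 10–12% of trials at OR 1.5, 17–21% at OR 2.0, 17–23% at OR 2.5 and 14–19% at OR 3.0. Simulating both tests jointly for the five distributions above gives about 6–25%.

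*The SAS code announced in 5.5.2.5 is not in the available text, and the table shells are separate files.* This is true, but the output descriptions and the list in SAP 10.1 leave no place for an ordinal result.

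**Conclusion.** The point holds as a cheap improvement, not as an error or a bias. The only planned between-arm test of CGIC and PGIC discards the order within 1–3 and within 4–7 and is conservative. Under a common shift at about 61 per arm this costs roughly 10–40% of power relative to an ordinal test, and part of that is due to Fisher's test rather than the grouping. The size rests on the assumed placebo distributions, the assumed effects and an even split of the 122 patients. An effect confined to the boundary between *no change* and *minimally improved* would reverse the ranking. The primary analysis is not touched.

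**What to change.** In SAP 5.5.2.5, add a between-arm comparison on all seven categories at Visits 4, 5 and 6. It can be a proportional-odds model with treatment as factor, reporting the common odds ratio with 95% CI and its direction, or a Wilcoxon rank-sum test. Keep the improved/not-improved table, with its odds ratio and Fisher p-value, alongside as supportive. Specify this before unblinding; if unblinding has already happened, report it as post hoc.

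The cost is a few lines of SAP text, one procedure call and one extra output per scale, and an update of the table list in 10.1 and the shells. The proportional-odds model needs a brief check of its assumption; the Wilcoxon test avoids that model but gives no common odds ratio. No new data and no change in conduct are needed.

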#### 5.5.2.6 Hauser's Parkinson Disease Diary

Functional status will be assessed via the Hauser's PD diary. Patient's will categorise their status every half-hour interval of the 24-hour day as: asleep, OFF, ON without dyskinesia, ON with non-troublesome dyskinesia, ON with trouble dyskinesia. The diary must be completed on the 3 days before Visit 2a,

I-DM-011SAP Page 29 of 49

Visit 2b (only if diary is not completed as instructed [more than 3 missing entries per day] at Visit 2a), Visit 4, Visit 5 and Visit 6/EDV.

The average ON/OFF-times of the last 3 diary days within 7 days before Visit 2a/ Visit 2b will be considered as the baseline value.

The average ON/OFF-time at each post-baseline visit will be calculated based on 3 diary entries closest to the target day within the analysis time window as defined in Section 4.8

The diary day begins at 6 AM and ends at 5:30 AM of the next day.

Percentage ON/OFF-time at baseline and each visit will be calculated as the ON/OFF-time as defined above, divided by the total time awake (calculated as the addition of all 30-minute periods in each day where the patient has recorded any state other than asleep).

If only diary data from less than 3 days are available for visit, the mean of the data from the available days will be used.

#### Handling of missing data:

If a day has less than 8 hours assessable waking time that day will be set to missing. In all other cases and in case of inconsistencies in the data, the following rules will be applied:

- If multiple states are recorded for one 30-minute period, the 30 minutes of the period will be equally divided among the multiple states, i.e. time with state X = 30 minutes / number of states recorded for this period.
- If a single entry of 30 minutes is missing within a day, adjacent available diary values carried forward and backward will be used for imputation of the missing record, i.e. 15 minutes will be allocated to the state of the adjacent periods, each. If any of the adjacent periods had multiple states recorded, these 15 minutes will be equally divided among the multiple states.
- If the first or last 30 minutes period of a day is missing, the state recorded immediately after or prior to this period, respectively, will be used for imputation of the missing record, using the same algorithm as described above.
- If two or more consecutive 30 minutes periods are missing within a day, these will not be imputed but set to missing.

Additionally, ON without troublesome dyskinesia will be summarised as ON with non-troublesome dyskinesia + ON without dyskinesia and ON-time will be summarised as ON without dyskinesia + ON with non-troublesome dyskinesia + ON with troublesome dyskinesia.

Responder analysis will be performed as:

- OFF-time responders: 1 hour or more reduction in OFF-time from baseline to each post-baseline visits.
- ON-time responders: 1 hour or more increase in ON-time from baseline to each post-baseline visit.

In addition, 1.5, 2, 2.5 hours reduction in OFF-time and increase in ON-time from baseline to all post-baseline visits will be calculated.

The following statistical output will be provided:

Table 15.2.7.1.1 Summary of Functional Status (Time in Minutes) – Full Analysis Set Table 15.2.7.1.2 Summary of Functional Status (Time in Minutes) – Per-Protocol Set

OFF, ON, ON with troublesome dyskinesia, ON without troublesome dyskinesia, ON with non-troublesome dyskinesia, ON without dyskinesia, asleep and change from baseline will be summarised for baseline and endpoint.

Table 15.2.7.2.1 Summary of Functional Status (Percentage) – Full Analysis Set Table 15.2.7.2.2 Summary of Functional Status (Percentage) – Per-Protocol Set

I-DM-011SAP Page 30 of 49

OFF, ON, ON with troublesome dyskinesia, ON without troublesome dyskinesia, ON with non-troublesome dyskinesia, ON without dyskinesia and change from baseline will be summarised for baseline and endpoint.

Table 15.2.7.3.1 Responder Analysis of OFF-time and ON-time – Full Analysis Set

Table 15.2.7.3.2 Responder Analysis of OFF-time and ON-time – Per-Protocol Set

OFF-time reduction and ON-time increase from baseline to each post-baseline visit will be summarised by defined responder categories.

Listing 16.2.3.6.1 Hauser's Parkinson's Disease Diary – Enrolled Set

Hauser's Parkinson's Disease Diary data will be listed for each patient in enrolled set.

Listing 16.2.3.6.2 Hauser's Parkinson's Disease Diary Analysis Parameters – Enrolled Set

Hauser's Parkinson's Disease Diary analysis parameters will be listed for each patient in enrolled set by analysis visit.

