At V2b (Day 1) and if eligibility is confirmed, the patient will be randomised to 50 mg opicapone or placebo once daily (1:1) and start treatment in addition to current treatment with L-dopa/DDCI.

Opicapone enhances the effects of L-dopa. Hence, it may be necessary to reduce the patient's L-dopa/DDCI dose within the first days or weeks of opicapone treatment. Therefore, the investigator will call the patient on Day  $8\pm 2$  (V3) to ask for any changes in the medical condition. If dose decrease of L-dopa/DDCI is deemed necessary, it may be adjusted by phone at V3 or an unscheduled on-site visit may be performed at the investigator's discretion. In case of L-dopa/DDCI adjustment an unscheduled phone call should be repeated up to 7 days after dose adjustment or V4 (Day  $29\pm 2$ ) should be performed, whatever applies first. The investigator can decrease the daily dose of L-dopa/DDCI (but keeping the number of daily intakes unchanged) as required until V4. If the investigator finds that the dose reduction was

too much, it can be increased again up to the baseline dose level. The dosage of L-dopa/DDCI should not be changed from V4 through the end of the study. No new anti-PD drugs should be started during the study and any that are ongoing at the start of the study must be kept at a stable dose throughout the study. No new pain medication should be started during the study except the allowed rescue medication. Baseline dose of pain medication may be reduced throughout the study if required due to pain medication-related AEs. If the investigator finds that the dose reduction was too much, it can be increased again up to the baseline dose level.

Further visits will be performed on Day  $85 \pm 4$  (V5, after 12 weeks) and Day  $169 \pm 4$  (V6, after 24 weeks). The primary analysis will be performed on the data collected at V6. A follow-up Visit (FU) will be performed on Day  $183 \pm 4$ , approximately 2 weeks after last intake of the investigational product (IP; 50 mg opicapone or placebo).

Patients who discontinue study participation prematurely will be asked to come to the site for an early discontinuation visit (EDV).

At V6 (or EDV, if applicable) the investigator will arrange for the patient's subsequent treatment, i.e. either prescribe further opicapone or switch to another treatment.

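### ON-time responders are defined on total ON-time, so the rule counts gains in troublesome dyskinesia and misses gains from its relief

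*SAP*

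**What the plan says.** All the definitions are in SAP section 5.5.2.6 (Hauser's Parkinson Disease Diary), under the paragraph on missing data.

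- Total ON-time: "ON-time will be summarised as ON without dyskinesia + ON with non-troublesome dyskinesia + ON with troublesome dyskinesia".
- A second derived quantity: "ON without troublesome dyskinesia will be summarised as ON with non-troublesome dyskinesia + ON without dyskinesia".
- The two responder rules: "OFF-time responders: 1 hour or more reduction in OFF-time from baseline to each post-baseline visits" and "ON-time responders: 1 hour or more increase in ON-time from baseline to each post-baseline visit".
- Further cut-offs on the same two variables: "In addition, 1.5, 2, 2.5 hours reduction in OFF-time and increase in ON-time from baseline to all post-baseline visits will be calculated".
- Content of responder Tables 15.2.7.3.1 and 15.2.7.3.2: "OFF-time reduction and ON-time increase from baseline to each post-baseline visit will be summarised by defined responder categories".

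ON without troublesome dyskinesia appears only in the continuous summaries. Tables 15.2.7.1.1 and 15.2.7.1.2 cover, in minutes, "OFF, ON, ON with troublesome dyskinesia, ON without troublesome dyskinesia, ON with non-troublesome dyskinesia, ON without dyskinesia, asleep and change from baseline". Tables 15.2.7.2.1 and 15.2.7.2.2 do the same in percentages, without sleep. All four are restricted to baseline and endpoint.

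The protocol synopsis lists diary functional status as secondary endpoint 11 and gives no responder definition. SAP section 5.5.2 treats secondary variables as exploratory.

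**The concern.** The diary records troublesome dyskinesia as a state of its own, and the SAP goes on to derive ON time without it. The ON responder rule then merges that state back in. A patient who exchanges OFF for troublesome dyskinesia is tabulated in the same way as one who exchanges OFF for ON without troublesome dyskinesia.

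The exchange cannot be dismissed as remote. The protocol synopsis (Methods / study design) states: "Opicapone enhances the effects of L-dopa. Hence, it may be necessary to reduce the patient's L-dopa/DDCI dose within the first days or weeks". A stronger L-dopa effect is a plausible route from OFF to dyskinesia, although neither document says how often this happens.

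At stake is how the responder tables can be read. They are the only tabulated patient-level classification that the SAP draws from the diary. As planned, they cannot separate the two kinds of gain. The OFF responder rule has no dyskinesia condition either, so it cannot separate them.

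**Working it through.** The plan states no responder rate or diary figure, so there is nothing of its own to reproduce. The check applies its rules to diary days with assumed hours. These illustrate the rule and are not trial data.

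Definitions:

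- Total ON = ON without dyskinesia + ON non-troublesome + ON troublesome.
- Good ON (shorthand here for ON without troublesome dyskinesia) = ON without dyskinesia + ON non-troublesome.
- Change = visit value − baseline value.
- ON responder at cut-off c: change in total ON ≥ c. OFF responder at c: change in OFF ≤ −c. The cut-offs are c = 1, 1.5, 2 and 2.5 h.
- Alternative ON responder at c: change in good ON ≥ c.

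Hours per day, baseline → visit:

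| Patient | OFF | Good ON | Troublesome ON | Total ON |
|---|---|---|---|---|
| A | 4.0 → 2.5 | 12.0 → 11.0 | 0 → 2.5 | 12.0 → 13.5 |
| B | 6.0 → 4.5 | 10.0 → 10.0 | 0 → 1.5 | 10.0 → 11.5 |
| C | 6.0 → 3.5 | 10.0 → 10.0 | 0 → 2.5 | 10.0 → 12.5 |
| D | 4.0 → 4.0 | 10.0 → 12.0 | 2.0 → 0 | 12.0 → 12.0 |
| E (sleep 8 → 7) | 6.0 → 6.0 | 10.0 → 10.0 | 0 → 1.0 | 10.0 → 11.0 |

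Results:

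- **A.** Total ON (11.0 + 2.5) − 12.0 = +1.5 h; OFF 2.5 − 4.0 = −1.5 h; good ON 11.0 − 12.0 = −1.0 h. The plan counts an ON and an OFF responder at 1 and 1.5 h, although good ON fell by an hour. Under the alternative this is a non-responder.
- **B.** Total ON +1.5 h, OFF −1.5 h, good ON 0 h. ON and OFF responder at 1 and 1.5 h under the plan; at no cut-off under the alternative.
- **C.** Total ON +2.5 h, OFF −2.5 h, good ON 0 h. ON and OFF responder at all four cut-offs under the plan; at none under the alternative.
- **D.** Total ON 12.0 − 12.0 = 0 h, OFF 0 h, good ON 12.0 − 10.0 = +2.0 h. Neither kind of responder at any cut-off under the plan; ON responder at 1, 1.5 and 2 h under the alternative.
- **E.** Total ON +1.0 h, OFF 0 h, good ON 0 h. ON responder at 1 h under the plan, through an hour less sleep spent in troublesome ON; at no cut-off under the alternative.

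Patients A, B, C and E are counted as ON responders without any gain in good ON. Patient D gains good ON and is not counted. The rule therefore errs in both directions.

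Scale only: SAP section 2.6 gives 122 patients in the full analysis set. Assuming an even split (122 / 2 = 61 per arm) and complete diaries, one reclassified patient moves an arm's rate by 1/61 = 1.6 percentage points. An assumed net 3 to 6 patients would move it by 3/61 = 4.9 to 6/61 = 9.8 points, up or down. The documents support no particular count in either arm, and it could be close to zero.

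What the other diary outputs show: responders are tabulated at each post-baseline visit, and SAP section 4.8 excludes Visit 3 from efficacy analysis, which leaves Visits 4, 5 and 6. The continuous tables cover baseline and endpoint only. At Visits 4 and 5 no diary table of troublesome ON stands beside the responder counts. At endpoint, group summaries cannot show which responders gained troublesome ON.

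**The case against.** The strongest case against is that this is a clear, internally consistent descriptive choice.

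- The table title refers to OFF-time and ON-time, and that is what the table measures. A patient with less OFF time is correctly an OFF responder by that definition. This stands: the limitation concerns interpretation, and the OFF rule itself needs no change.
- Troublesome dyskinesia is not hidden. The continuous diary tables separate it, MDS-UPDRS Part IV (motor complications) has its own repeated-measures analysis, CGIC and PGIC record overall status, and Listings 16.2.3.6.1 and 16.2.3.6.2 give diary data and analysis parameters by patient. A group-level shift would show at endpoint, and a reader could reconstruct individual responders from the listings. This stands too, but reconstruction by hand does not replace a tabulated row.
- Nothing confirmatory depends on these tables. They are exploratory, no test is named for them, and the primary endpoint is KPPS Domain 3. This stands in full.

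A reader might also infer that the rule inflates the opicapone ON responder rate relative to placebo. The documents do not support that. Patient D shows an error in the opposite direction, and placebo patients can be misclassified as well. The protocol passage on enhanced L-dopa effect also provides for lowering L-dopa/DDCI until Visit 4, which could reduce troublesome dyskinesia in some patients. The net direction between arms is unknown.

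**Conclusion.** The point holds as a limitation of definition. The ON responder rule counts gains in troublesome ON and ignores a move from troublesome ON to ON without it. This follows from the SAP's wording alone and needs no assumption about the data.

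Its numerical size cannot be stated. The documents contain no diary results, the worked patients use assumed hours, and the 61 per arm rests on an even split. The examples show that misclassification is possible, without showing that it is frequent or unequal between arms. It would go too far to say that the plan counts a harm as a treatment success: the SAP speaks of responders and of troublesome dyskinesia, and attaches no conclusion of the trial to these tables.

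The primary analysis and the sample size are unaffected. This is a cheap improvement, optional to low priority.

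**What to change.** Before unblinding, amend SAP section 5.5.2.6 and Tables 15.2.7.3.1 and 15.2.7.3.2 as follows.

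- Add ON responders defined on ON without troublesome dyskinesia, with increases of at least 1, 1.5, 2 and 2.5 h, at each post-baseline visit. Present this as the main ON responder measure, or at least beside total ON-time.
- Keep total ON-time responders in the table.
- Add one row for OFF responders with no increase in ON with troublesome dyskinesia.

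The cost is a few extra table rows. The variable is already derived and no new data are needed. The resulting ON responder rates may be higher or lower than those on total ON-time. Adding the rows after unblinding would make them post hoc.
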